		5.1 Storage	
		5.2 Dispensing of Study Drug	
		5.3 Return or Destruction of Study Drug	
6	\mathbf{S}	ΓUDY PROCEDURES	13
	6.1	Day 0	13
	6.2	Day 1	
	6.3	DAY 2	
	6.4	DAY 3	
	6.5	SCHEDULE OF EVENTS	
7	S	TATISTICAL PLAN	. 17
	7.1	SAMPLE SIZE DETERMINATION	
	7.2	STATISTICAL METHODS	
	7.3	SUBJECT POPULATION(S) FOR ANALYSIS	. 18
8	\mathbf{S}	AFETY AND ADVERSE EVENTS	. 18
	8.1	Definitions	18

8.2	RECORDING OF ADVERSE EVENTS	20
8.3	REPORTING OF SERIOUS ADVERSE EVENTS AND UNANTICIPATED PROBLEMS	20
8	3.3.1 Sponsor-Investigator reporting: notifying the Mayo IRB	21
8.4	STOPPING RULES	22
8.5	MEDICAL MONITORING	
9 D	DATA HANDLING AND RECORD KEEPING	22
9.1	CONFIDENTIALITY	22
9.2	SOURCE DOCUMENTS	
9.3	CASE REPORT FORMS	
9.4	RECORDS RETENTION	
10 S	STUDY MONITORING, AUDITING, AND INSPECTING	24
10.1	STUDY MONITORING PLAN	24
10.2		
11 E	ETHICAL CONSIDERATIONS	25
12 S	STUDY FINANCES	25
12.1	FUNDING SOURCE	25
13 P	PUBLICATION PLAN	25
	REFERENCES	

List of Abbreviations

LIST OF ABBREVIATIONS

AE Adverse Event/Adverse Experience

CFR Code of Federal Regulations

CRF Case Report Form

DSMB Data and Safety Monitoring Board FDA Food and Drug Administration

GCP Good Clinical Practice

HIPAA Health Insurance Portability and Accountability Act

IB Investigator's Brochure

IND Investigational New Drug Application

IRB Institutional Review Board PHI Protected Health Information

PI Principal Investigator

SAE Serious Adverse Event/Serious Adverse Experience

SOP Standard Operating Procedure

Study Summary

Title	Comparison of F-18 FDG PET CT and PET MRI with C-11 acetate PET CT and PET MRI in the diagnosis of active multiple myeloma disease: a Pilot Study				
Running Title	C-11 acetate vs. FDG with PET/CT and PET/MRI in Myeloma				
Protocol Number	16-007867				
Phase	Pilot study				
Methodology	Prospective observational repeated-measure study design				
Overall Study Duration	12 weeks				
Subject Participation Duration	Approx. 270 minutes, over 2 days, in the nuclear medicine suite.				
Single or Multi-Site	Single				
Objectives	1. Our primary interest is to investigate which tracer and imaging technique combination (FDG PET/MRI, C11 PET/CT, C11 PET/MRI) can detect more clinically significantly MM lesions compared to the standard technique (FDG PET/CT). 2. Secondary Objectives: Evaluate which tracer and imaging technique combination (FDG PET/CT, FDG PET/MRI, C11 PET/CT, C11 PET/MRI) best distinguishes the clinically significant MM lesions from other lesions detected.				

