3.1 General Description

Our investigation is titled *Comparison of F-18 FDG PET CT and PET MRI with C-11 acetate PET CT and PET MRI in the diagnosis of active multiple myeloma disease: a Pilot Study.* This study will be a prospective, observational repeated-measure study to compare the standard technique of F-18 FDG PET/CT with the study techniques of F-18 FDG PET/MRI, C-11 acetate PET/CT and C-11 acetate PET/MRI in the detection of active multiple myeloma in human patients. This pilot study of 10 patients will help guide development of a subsequent future prospective study involving a larger cohort of patients. The doses of C-11 acetate will be administered intravenously. F-18 FDG is already an FDA-approved intravenous radiopharmaceutical. We anticipate study duration of 12 weeks, if patient recruitment proceeds as expected.

Our primary interest is to investigate which tracer and imaging technique combination (FDG PET/MRI, C11 PET/CT, C11 PET/MRI) detects the greatest number of clinically significantly MM lesions compared to the standard technique (FDG PET/CT).

[figure not shown]
Our secondary objective is to evaluate which tracer and imaging technique combination (FDG PET/CT, FDG PET/MRI, C11 PET/CT, C11 PET/MRI) best distinguishes the clinically significant MM lesions from other lesions detected.

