3.2 Number of Subjects

Ten subjects who have completed all phases of the protocol are required. In order to ensure this, it may be necessary to screen a small number of additional candidates, perhaps up to 5 total, to ensure we reach our study target of ten complete studies. For example, if an enrolled subject cannot or will not return for the second day of imaging, we will recruit and enroll a replacement subject.

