3.5 Secondary Study Endpoints

Evaluate which tracer and imaging technique combination (FDG PET/CT, FDG PET/MRI, C11 PET/CT, C11 PET/MRI) best distinguishes the clinically significant MM lesions from other lesions detected.

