7.1 Sample Size Determination

When the sample size is 10, as planned in this pilot study, a single-group repeated measures analysis of variance with a 0.05 significant level will have 80% power to detect a difference in means across the 4 levels by an effect size of 0.32. Assuming a standard deviation at each level to be 2.2 and a between level correlation to be 0.6, the average difference will be detected in this scenario is 0.78.

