7.2 Statistical Methods

Descriptive Statistics

Primary Hypothesis: There is no difference in the number of clinically significant MM lesions detected by FDG PET/MRI, C11 PET/CT, C11 PET/MRI compared to the standard technique FDG PET/CT.

The patients will go through all of the 4 techniques and the number of clinically significant MM lesions detected by each technique will be collected. Our primary outcome is the number of MM lesions detected by each technique, which can vary from 0 to 13 with 5 or 6 lesions as an average for the MM patients. It is a repeated measures ANOVA design and our primary interest if to see if there is a within subject effect – if the number of MM lesions detected by each technique differ.

If the overall test is significant, post-hoc comparisons between the scores of the three new techniques (FDG PET/MRI, C11 PET/CT, C11 PET/MRI) and the standard technique (FDG PET/CT) will be carried out with Bonferroni correction for multiple comparison.

Secondary Hypothesis 1: There is no difference in the clarity scoring of the MM lesions among the 4 techniques.

The primary interest of Objective 2 is to compare the clarity of the detected MM lesions across the 4 techniques. A score demonstrating clarity of the lesion will be assigned to each detected lesion with higher score means clearer of the lesion image. One way repeated measure analysis of variance will be employed to detect if there is any difference among the average scores of detected MM lesion in each technique. If the overall test is significant, post-hoc comparisons between the scores of the three new techniques (FDG PET/MRI, C11 PET/CT, C11 PET/MRI) and the standard technique (FDG PET/CT) will be carried out with Bonferroni correction for multiple comparison.

Explore Objectives:

Explore which are the risk factors for having more MM lesions: CMP (Comprehensive Metabolic Panel) Glucose, Calcium, Proteins, Albumin, Total Protein, Sodium, Potassium, CO2 (carbon dioxide, bicarbonate), Chloride, BUN (blood urea nitrogen), Creatinine, ALP (alkaline phosphatase), ALT (alanine amino transferase), AST (aspartate amino transferase), Bilirubin;

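### Objective 2 asks which of four techniques is best, but no planned contrast compares two new techniques, and the tracer contrast is planned on PET/CT only

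*Combined protocol and SAP*

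**What the plan says.** The secondary endpoint (Section 3.5, repeated in Section 2 and the Study Summary) is to "Evaluate which tracer and imaging technique combination (FDG PET/CT, FDG PET/MRI, C11 PET/CT, C11 PET/MRI) best distinguishes the clinically significant MM lesions". All four combinations are listed, FDG PET/CT included.

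Section 7.2 tests the clarity score with a four-level one-way repeated-measures ANOVA. If that is significant, the follow-up is "post-hoc comparisons between the scores of the three new techniques (FDG PET/MRI, C11 PET/CT, C11 PET/MRI) and the standard technique (FDG PET/CT", with Bonferroni correction. The same sentence stands under the primary hypothesis on lesion counts, and the Multiplicity paragraph repeats the three comparisons for counts. No other contrast between techniques is planned. The exploratory regression concerns laboratory risk factors.

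The primary objective is worded differently: it asks which of the three new techniques detects more significant lesions than FDG PET/CT.

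The running title in the Study Summary is "C-11 acetate vs. FDG with PET/CT and PET/MRI in Myeloma". On purpose, Section 3.1 says: "This pilot study of 10 patients will help guide development of a subsequent future prospective study". On completeness, Section 3.2 says: "Ten subjects who have completed all phases of the protocol are required", and Section 7.3 restricts the analysis to completers. Each analysed patient therefore supplies all four cells of a two-tracer by two-scanner layout.

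**The concern.** For Objective 2 the question and the follow-up tests do not match. The overall test can show that the four techniques differ, and the three contrasts can show that a new technique differs from the standard. If two or three of them do, nothing planned separates them, and that is the case in which the question of a best technique matters most.

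A second, smaller gap concerns attribution. Acetate PET/MRI is compared only with FDG PET/CT, which differs from it in both tracer and scanner. The plan does not ask whether acetate gains over FDG on PET/MRI, how large the tracer difference is over both scanners, or whether it depends on the scanner. A larger study would be designed on those quantities. If they are added after the data are seen, they will be post hoc.

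**Working it through.** **1. The six possible pairs, set against Section 7.2**

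| Pair | What changes | Planned |
|---|---|---|
| C11 PET/CT vs FDG PET/CT | tracer | yes |
| FDG PET/MRI vs FDG PET/CT | scanner | yes |
| C11 PET/MRI vs FDG PET/CT | both | yes |
| C11 PET/MRI vs FDG PET/MRI | tracer | no |
| C11 PET/MRI vs C11 PET/CT | scanner | no |
| C11 PET/CT vs FDG PET/MRI | both | no |

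The three unplanned pairs are exactly the new-versus-new ones.

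**2. Inputs and the plan's own figure (Section 7.1)**

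The plan claims that "a single-group repeated measures analysis of variance with a 0.05 significant level will have 80% power"; the effect it has in mind is 0.32 over the four techniques. Its inputs are: "Assuming a standard deviation at each level to be 2.2 and a between level correlation to be 0.6". The sample size is n = 10.

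Take the effect size as V / [SD²(1 − ρ)], where V is the variance of the four means (divisor 4).
- Noncentrality = 10 × 4 × 0.32 = 12.8 on 3 and 27 df, which gives power 80.6%. The stated 80% reproduces.
- √V = √(0.32 × 4.84 × 0.4) = 0.787, against the plan's 0.78. That figure is therefore the SD of the four means, not a pairwise difference.
- In a pure tracer effect, two means sit at one value and two sit D higher, so √V = D/2 and D = 2 × 0.787 = 1.57 lesions.

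**3. Precision for lesion counts**

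SD²(1 − ρ) = 4.84 × 0.4 = 1.936. The t quantile on 9 df is 2.262.
- One pair: SE = √(2 × 1.936/10) = 0.622; half-width 2.262 × 0.622 = 1.41.
- Pooled tracer contrast (mean of two acetate minus mean of two FDG): SE = √(1.936/10) = 0.440; half-width 1.00.
- Interaction (difference of the two tracer differences): SE = √(4 × 1.936/10) = 0.880; half-width 1.99.

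**4. Power for a pure tracer effect of 1.57 lesions (noncentral t, 9 df, two-sided)**

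| Alpha | Pooled tracer contrast | One pair |
|---|---|---|
| 0.05 | 88.8% | 61.6% |
| 0.0167 (0.05/3) | 72.7% | 39.7% |

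The fair comparison is along a row.

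**5. Sensitivity to the correlation structure (assumed values)**

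The plan gives one correlation for all pairs. Suppose same-tracer scans correlate 0.8 and cross-tracer scans 0.5; the average over six pairs is (2 × 0.8 + 4 × 0.5)/6 = 0.6, as planned.
- Pooled contrast: variance = 4.84 × [(1 + 0.8) − 2 × 0.5] = 3.872; SE = √0.3872 = 0.622; power at 0.05 is 61.6%.
- One same-scanner tracer pair: variance = 2 × 4.84 × 0.5 = 4.84; SE = 0.696; power 52.4%.

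With 0.7 and 0.55, the pooled power is 74%. The pooled contrast still has the smaller SE, but most of its advantage can disappear.

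**6. A rule for naming a best technique**

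Rule: a technique is called best only if its unadjusted 95% intervals against all three others exclude zero in its favour. Simulated with the inputs above and no preceding overall test, the chance of falsely naming a single best was about 0.5% with all four equal, 1.1% with three tied at the top and 5% with two tied at the top. Success is demanding: 80% power for one pair at 0.05 needs 1.96 lesions, and for one of six Bonferroni-corrected pairs (0.05/6) it needs 2.70.

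**The case against.** The strongest reply is that the plan already contains two clean single-factor contrasts. C11 PET/CT against FDG PET/CT changes only the tracer, and FDG PET/MRI against FDG PET/CT changes only the scanner. A reader might infer from the list of contrasts that acetate is never tested against FDG, but the documents do not support that. Nor do the primary contrasts mismatch the primary objective, which is worded against the standard. No stated objective asks for a tracer effect averaged over scanners; that interest comes from the titles. This part of the reply stands.

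A reader might also set 88.8% against 39.7% as the gain from pooling. That mixes alpha 0.05 with 0.0167, and both figures assume no interaction and a common correlation of 0.6.

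A further limit is that the layout is not a clean factorial. By Sections 6.2 and 6.3, FDG is always on Day 1 and acetate on Day 2, up to 14 days later (Section 3.3), and PET/CT always precedes PET/MRI. FDG PET/MRI is a later image of the same injection, whereas acetate PET/MRI uses a second injection imaged from ten minutes. Tracer is thus confounded with day, and scanner with order and, for FDG, with uptake time. The planned contrasts share this limit, so it is no reason to omit the others, but causal attribution would be too much to claim.

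Finally, main effects do not identify the best of four techniques; pairwise differences are needed, and power is low with ten patients. That favours estimates with intervals over more tests.

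**Conclusion.** The point holds in a limited form. Objective 2 asks for the best of four, and its follow-up contrasts cannot answer when more than one new technique beats FDG PET/CT. In addition, there is no acetate-versus-FDG contrast on PET/MRI, no pooled tracer effect and no interaction, although the same scans supply them.

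For lesion counts, pooling narrows the 95% half-width from 1.41 to 1.00 and, at equal alpha, raises power from 61.6% to 88.8% (0.05) or from 39.7% to 72.7% (0.0167). This rests on normality, SD 2.2, a common correlation of 0.6 and a pure tracer effect of 1.57 lesions. Under the assumed 0.8/0.5 correlations, pooled power is about 62%. The documents give no SD for the clarity score, so no size can be put on the Objective 2 gap.

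This is a desirable improvement to the secondary analyses of a pilot. It does not undermine the primary test.

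**What to change.** Leave the primary test and its three Bonferroni comparisons unchanged. Add to Section 7.2, before analysis, as secondary analyses:

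1. For Objective 2, the three new-versus-new differences in clarity score with 95% CIs. State that a technique is called best only if its unadjusted 95% intervals against all three others, FDG PET/CT included, exclude zero in its favour, and that otherwise no best technique is named.
2. The pooled tracer contrast, the tracer difference within each scanner and the tracer-by-scanner interaction, each with a 95% CI.
3. A statement that tracer and scanner effects are confounded with fixed order (FDG before acetate by up to 14 days, PET/CT before PET/MRI) and with uptake time, because the FDG PET/MRI reuses the PET/CT injection and the acetate PET/MRI does not.

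The cost is a few lines of text and a few more estimates from the same scans. Power to name a best technique stays low at n = 10. The interaction is imprecise (80% power at 0.05 needs 2.77 lesions), and if it is large the pooled effect must be read within scanner.

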Number of Subjects	10				
Diagnosis and Main Inclusion Criteria	Clinically diagnosed multiple myeloma spectrum disease. Adult patients who are able to provide informed consent.				
Study Product, Dose, Route, Regimen	C-11 acetate, 10 mCi, intravenous injections				
Duration of Administration	Bolus injection				
Reference therapy	F-18 FDG				
Statistical Methodology	Objective 1. Repeated measures ANOVA. Univariate one-way repeated measures ANOVA F-test is used to calculate the sample size. Objective 2. One way repeated measure analysis of variance will be employed to detect if there is any difference among the average scores of detected MM lesion in each technique. When the sample size is 10, a single-group repeated measures analysis of variance with a 0.05 significant level will have 80% power to detect a difference in means across the 4 levels by an effect size of 0.32.				

1 Introduction

This document is a protocol for a human research study. This study will be carried out in accordance with the applicable United States government regulations and Mayo Clinic research policies and procedures.

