1.1 Background

This project will study differing radiopharmaceutical and imaging approaches in patients with multiple myeloma spectrum disease. The use of carbon-11 (C-11) acetate as a positron emission tomography (PET) tracer to detect multiple myeloma has shown promise in a small number of recent research publications. The current standard clinical PET tracer being used, F-18 fluorodeoxyglucose (F-18 FDG), has some limitations due to the fact that up to 30% of myelomas do not show increased glucose pathway activity. In these patients, recent reports suggest that exploiting the intracellular acetate pathway rather than the glucose pathway may more reliably detect the presence of active myeloma deposits.

The study would include any consent-able adult patient over the age of 20 who is scheduled for a diagnostic FDG PET/CT scan for evaluation of multiple myeloma (MM) for the following indications: new diagnosis, high risk smoldering MM, relapse as defined by investigator.

Acetate is a key component in cellular reactions which result in the oxidative metabolism (via participation in the citric acid cycle in mitochondria), synthesis of fatty acids (in production of cell membranes), and in nuclear histone acetylation (which regulates gene expression). Cell membrane synthesis and gene expression are both important upregulated functions within cancer cells. Intravenously injected C-11 acetate is a radiopharmaceutical which acts identically to normal non-radioactive C-11 acetate in the body. The radioactivity associated with the acetate metabolic pathways can be imaged with positron emission tomographic devices, revealing and permitting visual differentiation of benign versus cancerous tissue by a radiologist.

Our study also incorporates use of a new FDA-approved hybrid PET/MRI technique. This additional modality will permit a four-way technique comparison combination which has not to date been reported.

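### The secondary objective asks which technique best separates MM lesions from other lesions, but the planned test compares only the clarity of MM lesions

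*Combined protocol and SAP*

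**What the plan says.** The secondary objective appears in the Study Summary and in Sections 2 and 3.1, and Section 3.5 repeats it as the secondary endpoint. In all four places the question is which technique "best distinguishes the clinically significant MM lesions from other lesions detected". No metric is attached.

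Section 7.2 restates the aim: "The primary interest of Objective 2 is to compare the clarity of the detected MM lesions across the 4 techniques". Its Secondary Hypothesis 1 is "There is no difference in the clarity scoring of the MM lesions among the 4 techniques". On data collection it says "A score demonstrating clarity of the lesion will be assigned to each detected lesion", with higher scores meaning a clearer image. The analysis is a one-way repeated measures ANOVA looking for "any difference among the average scores of detected MM lesion in each technique". If that is significant, each of the three new techniques is compared with FDG PET/CT under a Bonferroni correction. The Study Summary's method entry for Objective 2 gives the same analysis.

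**The concern.** Distinguishing one kind of lesion from another is a two-class question, and its answer depends on how both kinds look on a technique. The planned analysis uses one class. It can say whether MM lesions are rated clearer on one technique than on another, but it carries no information on whether the other lesions are rated clearer too, or less clear, or the same.

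At stake is the claim attached to the result. If the clarity comparison is reported against the endpoint in Section 3.5, a significant F test would be read as evidence of better discrimination and a non-significant one as evidence of no difference in discrimination. Neither follows. The claim could travel further, because Section 3.1 says the pilot "will help guide development of a subsequent future prospective study involving a larger cohort of patients".

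**Working it through.** **1. The plan's own figure.** Section 7.1 gives 80% power for n = 10, four levels, alpha 0.05 and effect size 0.32, and the Study Summary repeats this beside Objective 2. Take the effect size as V / [SD² × (1 − ρ)], where V is the variance of the level means. The noncentrality is then 10 × 4 × 0.32 = 12.8 on 3 and 27 degrees of freedom, and power is 0.806. With SD 2.2 and correlation 0.6, √V = √(0.32 × 2.2² × 0.4) = 0.787, against the stated 0.78. The figure reproduces. It does not bear on this point, which concerns what is tested and not how powerfully.

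**2. Objective and analysis side by side.**

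| Element | Stated objective and endpoint | Section 7.2 analysis |
|---|---|---|
| Lesions used | Clinically significant MM lesions and other detected lesions | Detected MM lesions |
| Quantity | How well the two kinds are told apart | Average clarity score |
| Comparison | Which of four is best | Overall F test, then three techniques each against FDG PET/CT |

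The rows differ in lesions, quantity and comparison. The post-hoc contrasts also do not rank all four techniques.

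**3. Do other lesions enter elsewhere?** The primary outcome is a count of MM lesions per technique, and the exploratory regression models the same count. Neither uses other lesions. No AUC, specificity or MM-versus-other comparison is planned.

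**4. What the test can and cannot see.** For technique t, let m(t) be the mean clarity of MM lesions and o(t) that of other lesions. The planned test compares m(t) across t. Separation depends on m(t) − o(t).
- If one technique raises m and o by the same amount, m(t) differs but m(t) − o(t) does not. The test can reject with separation unchanged.
- If only o changes, m(t) is constant but m(t) − o(t) differs. The test has nothing to detect.

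An illustration with invented scores (normal, SD 1 in both kinds; none of these values is in the documents) uses AUC = Φ[(m − o) / (SD × √2)]:

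| m | o | m − o | AUC | MM clarity against first row |
|---|---|---|---|---|
| 3 | 2 | 1 | 0.760 | – |
| 4 | 3 | 1 | 0.760 | higher |
| 4 | 4 | 0 | 0.500 | higher |
| 3 | 1 | 2 | 0.921 | unchanged |

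MM clarity can rise while separation stays the same or disappears, and separation can improve while MM clarity does not move. The table shows direction only and says nothing about likely size in this trial.

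**The case against.** The best defence is that this is a labelling gap. Section 7.2 says openly that the interest of Objective 2 is clarity, and the test answers the hypothesis that section names. Harm arises only if the result is later reported under the wider wording, and nothing in the documents commits the sponsor to that. This stands as a limit on severity. It does not remove the conflict, because the endpoint in Section 3.5 is still discrimination and the document leaves two incompatible definitions of one objective.

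A second defence is that a score goes to every detected lesion, so other lesions may be rated. They may be; the text leaves this open, and a reader who infers that they will not be scored goes too far. But the hypothesis, the analysed average and the contrasts are all confined to MM lesions, so any such scores would not be used.

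Third, the other lesions in the objective need not be non-MM: they could include MM lesions that are not clinically significant. The Objective 2 text in Section 7.2 drops that qualifier, so such lesions could sit inside the average. That reading does not help, since pooling two kinds of lesion is not contrasting them.

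A reader might also take the specificities in Section 1.4 (100% for C-11 acetate, 93.1% for FDG) as a measure of what the planned test would miss. The documents do not support that. The unit is not stated, and if it is the patient, the figures concern people without myeloma and not other lesions within the myeloma patients enrolled here.

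**Conclusion.** Wrong as written, and worth fixing before results are reported. The planned analysis cannot answer the only stated secondary objective and endpoint, because it never contrasts clinically significant MM lesions with other lesions, of whichever kind. This rests on the text and on the logic above and needs no assumption about score distributions.

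The size of the resulting error cannot be computed: the documents give no clarity scale, no SD for clarity scores and no expected number of other lesions. A reader might infer that the trial's main conclusion is compromised. It is not: the primary endpoint is a count of MM lesions with its own test, and the sample size and safety monitoring do not depend on this objective.

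**What to change.** **Reword the objective.** In the Study Summary and Sections 2, 3.1 and 3.5, replace the secondary objective and endpoint with the question Section 7.2 tests, for example: *Compare clarity scores of detected MM lesions between the four techniques.* Add a sentence that no conclusion will be drawn about distinguishing MM lesions from other lesions. Choose one term, either MM lesions or clinically significant MM lesions, and use it in both the objective and the Objective 2 text of Section 7.2; otherwise the rewording creates a new mismatch. This costs edits in four places, a possible change of term in Section 7.2, and a narrower secondary claim.

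**If the sponsor prefers to keep the discrimination objective,** Section 7.2 must add an analysis that uses both kinds of lesion, such as a per-patient MM-minus-other score difference or a patient-clustered AUC, with comparisons among all four techniques and not only against FDG PET/CT. It should be reported as exploratory. Other lesions may be few in 10 patients, and the documents describe no lesion-level reference standard for deciding which lesions are which. The cost is scoring and classifying every detected lesion on 40 scans (10 patients × 4 techniques), for an estimate likely to be imprecise.

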SPEP (Serum Protein Electrophoresis). Immunoglobulins, Serum Free light chains; Bone marrow biopsy % and beta-2-microglobulin level (if obtained). Linear regression model with correlated data (the MM lesions detected by each technique) will be utilized to investigate the association between the potential risk factors and the number of MM lesions detected for each patient.

Handling of Missing Data

Since our sample size is 10, and they will get their imaging done in two days, we don't anticipate any missing data.

Multiplicity

We only have one primary outcome for our primary research interest. There will be no concern of multiple testing for the overall group testing. But if we see an overall effect and we will do post-hoc comparisons of the numbers of detected MM lesions between the three new techniques (FDG PET/MRI, C11 PET/CT, C11 PET/MRI) and the standard technique (FDG PET/CT). Bonferroni correction for multiple comparison will be used to address multiplicity issue.

Interim Analysis

There will not be interim analysis for our study.

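### Clarity is undefined where a technique detects no lesion, so the Objective 2 repeated-measures ANOVA can lose fully scanned patients, and lose them selectively; the missing-data paragraph overlooks this

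*Combined protocol and SAP*

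**What the plan says.** Section 7.2, Secondary Hypothesis 1, defines the Objective 2 measure: "A score demonstrating clarity of the lesion will be assigned to each detected lesion". The scores are averaged per technique, and the four averages are compared by one-way repeated-measures ANOVA. No scale is given, and no value is set for a technique that detects nothing.

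Under the primary hypothesis, the same section gives the lesion count per technique a range of 0 to 13, with an average of 5 or 6.

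The missing-data paragraph of section 7.2 anticipates no missing data. Its stated reason is "Since our sample size is 10, and they will get their imaging done in two days". It gives no method for a missing value.

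The Study Summary, under Objective 2, states "When the sample size is 10, a single-group repeated measures analysis of variance with a 0.05 significant level will have 80% power" for an effect size of 0.32 across four levels. Section 7.1 repeats this without naming an objective, and adds an SD of 2.2 per level, a between-level correlation of 0.6 and a detectable average difference of 0.78.

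Sections 3.2 and 4.4 replace patients who withdraw or do not complete imaging. Section 7.3 analyses those who completed all procedures and follow-up. Section 1.1 gives as the rationale that "up to 30% of myelomas do not show increased glucose pathway activity".

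**The concern.** A mean over zero lesions does not exist. A patient can complete every scan, count as a completer under section 7.3, not qualify for replacement, and still lack a clarity value for one technique. The standard one-way repeated-measures ANOVA needs all four values, so without a rule the whole patient is lost, including the scores from the techniques that did show lesions.

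Two things are at stake. The first is what the result describes. A patient with lesions on one technique and none on another shows the largest contrast between techniques, and that patient is the one removed. Objective 2 would then describe clarity only in patients already visible on every technique. The second is precision, because the power statement placed under Objective 2 assumes 10 patients. With no rule in the plan, the analyst would also have to choose one after seeing the data.

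**Working it through.** **Inputs.** n = 10, alpha 0.05, k = 4 techniques, effect size 0.32, SD 2.2, correlation 0.6, average difference 0.78 (Study Summary and section 7.1). Lesion count 0 to 13, average 5 or 6 (section 7.2). The documents give no rate of patients without a lesion on at least one technique, so that rate is an assumption and is shown as a range.

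**Step 1: reproduce the stated power.** Read the effect size as the variance of the four means divided by SD²(1 − correlation). Then:
- implied SD of the means = √(0.32 × 2.2² × 0.4) = √0.6195 = 0.787, against the stated 0.78, which supports this reading;
- noncentrality = n × k × 0.32 = 10 × 4 × 0.32 = 12.8;
- degrees of freedom = 3 and 3(n − 1) = 27;
- power from the noncentral F, assuming sphericity = 80.6%.

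The stated 80% reproduces. Reading 0.32 as Cohen's f, with noncentrality n × k × f²/(1 − correlation), gives 70.4% and does not match.

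**Step 2: power by number of complete patients,** same formula and effect size:

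| Patients with all four averages | Power | Effect size needed for 80% |
|---|---|---|
| 10 | 80.6% | 0.315 |
| 9 | 75.1% | 0.357 |
| 8 | 68.4% | 0.411 |
| 7 | 60.4% | 0.485 |

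**Step 3: average over the number retained.** For a per-patient loss rate p, weight the power at x patients by the binomial probability C(10, x)(1 − p)^x p^(10 − x). The chance of losing at least one patient is 1 − (1 − p)^10.

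| Assumed loss rate | Chance of losing at least one | Average complete-case power |
|---|---|---|
| 1% | 10% | 80% |
| 5% | 40% | 78% |
| 10% | 65% | 75% |
| 20% | 89% | 67% |
| 30% | 97% | 59% |

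**Step 4: which rates fit the plan's own figures?** Take the SD of 2.2 to be on the lesion-count scale, as it appears to be.
- With mean 5.5, the chance of a zero on one technique is e^(−5.5) = 0.4% under a Poisson count, or Φ((0.5 − 5.5)/2.2) = 1.2% under a normal approximation. Over four techniques the per-patient chance is at most four times that: 1.6% to 4.6%.
- As a ceiling, if a share q of patients has zero and the overall mean is m, the SD is at least m√(q/(1 − q)). Hence q ≤ 2.2²/(2.2² + m²): 4.84/29.84 = 16% at m = 5 and 4.84/40.84 = 12% at m = 6. The ceiling is reached only if all other patients have identical counts.
- A 30% share of zeros on one technique would need an SD of at least 5 × √(0.3/0.7) = 3.3, or 3.9 at m = 6.

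The ceiling applies to each technique. Loss on any technique could exceed it if different techniques missed different patients, but the assumed correlation of 0.6 points the other way.

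**Limit of the arithmetic.** Steps 2 and 3 hold the effect at 0.32, so they treat the loss as random. They measure the loss of numbers, not the distortion from selective loss.

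**The case against.** The plan does not say that such a patient is dropped; that is the default of the named test when no rule is given. The plan's mean and SD make zero counts uncommon. The power statement is tied to Objective 2 only by its position in the Summary, and no clarity scale or SD is given, so the 80% carries over only through the standardised effect size. This is also a secondary objective in a 10-patient pilot. All of this stands, and it keeps the size modest. It does not supply the missing rule or make the loss random.

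A reader might infer from section 1.1 that about 30% of patients will have no FDG lesion, leaving 7 patients and 60% power. The documents do not support that. The 30% is an upper figure for low glucose activity. Nowhere is it equated with zero lesions scored on FDG PET/CT or PET/MRI, where the CT or MRI component may still show one. It also conflicts with the plan's own mean and SD (step 4).

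A reader might also infer that a mixed model alone cures the problem. It keeps the patient's other scores, but it treats the absent score as ignorable when non-detection is the reason for its absence.

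**Conclusion.** The gap is real and follows from the plan's own definitions: an Objective 2 value can be absent with every scan done, the named ANOVA then loses the patient, and the missing-data paragraph does not recognise it. The selectivity matters more than the power. At assumed loss rates of 1% to 10%, average complete-case power goes from about 80% to 75%. Losing one patient gives 75%, and losing two gives 68%. The 30% rate (about 59%) is an extreme case outside the plan's planning values. These figures assume sphericity, an unchanged effect of 0.32 and random loss. The primary objective is unaffected, because a count of 0 is a valid observation. The point deserves a change to the plan, but it does not threaten the study's main result.

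**What to change.** 1. Correct the missing-data paragraph in section 7.2 to say that an Objective 2 value is absent whenever a technique detects no lesion, even with all imaging complete.
2. Replace the Objective 2 ANOVA with a mixed model of the available clarity scores, with technique as a fixed effect and a patient effect, so that a patient unscored on one technique still contributes the other scores.
3. Add a sensitivity analysis that gives non-detection the lowest clarity score, for example over all lesions found by any technique. This is needed because the absence is not ignorable.
4. Report the number of patients without a score for each technique beside the result.
5. In the Summary, state that the 80% holds only if all 10 patients have a score on all four techniques. Do not enter 60% to 75% as the power of the mixed model: those are complete-case ANOVA figures, and no mixed-model power has been calculated.

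The cost is a few sentences in section 7.2 and the Summary, slightly more analysis work and a more qualified power statement. No extra patients, scans or visits are needed, and section 7.2 already plans a correlated-data model for its exploratory objective.
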